6. POPULATION OF ANALYSIS

6.1. ANALYSIS POPULATION PRIMARY

All enrolled participants will be included in the primary analysis.

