5.1.5 SAMPLE SIZE AND STATISTICAL POWER

The sample size is 300 participants, made up of 100 cases and 200 controls. Sample power is calculated according to the following assumptions:

- Median antibody titers in controls are estimated at 898 mfi (*mean fluorescence intensity*). This estimate is based on a previous study in which antibody titres against CSP were determined by the same Luminex technology in a malaria-endemic context [17].
- The logarithm of the anti-malarial anti-CSP antibody levels of the controls is normally distributed, with a mean of 6.8 and a standard deviation of 1.
- The logarithm of malaria antibody levels in cases is normally distributed with a standard deviation of 1.
- For each case, two matched controls are recruited.

PROTOCOL: MALARIA AS A PROTECTIVE FACTOR AGAINST SEVERE COVID-19 IN THE DEMOCRATIC REPUBLIC OF CONGO

- The correlation between the logarithm of anti-malarial antibody levels in cases and matched controls is 0.7.

The data collected will be analyzed using conditional logistic regression with a two-tailed test at the 5% significance level.

Power is calculated for different effect sizes (i.e. difference in malaria antibody levels between cases and controls). The table below shows the power for different effect sizes, or rather design effects. With a sample size of 300, the study is able to detect a 17% difference in median antibody titres with 80% power, which is considered clinically relevant.

Mean of logarithm of anti-malarial antibody levels in controls	Average of the logarithm of anti-malarial antibody levels in cases	Median malaria antibody levels of controls	Median malaria antibody levels of cases	Power
6.8	6.7	898	812	0.3
6.8	6.69	898	804	0.35
6.8	6.68	898	796	0.4
6.8	6.67	898	788	0.48
6.8	6.66	898	781	0.53
6.8	6.65	898	773	0.6
6.8	6.64	898	765	0.65
6.8	6.63	898	757	0.7
6.8	6.62	898	750	0.76
6.8	6.61	898	742	0.81

PROTOCOL: MALARIA AS A PROTECTIVE FACTOR AGAINST SEVERE COVID-19 IN THE DEMOCRATIC REPUBLIC OF CONGO

6.8	6.6	898	735	0.83
6.8	6.59	898	728	0.87
6.8	6.58	898	721	0.9
6.8	6.57	898	713	0.93
6.8	6.56	898	706	0.94
6.8	6.55	898	699	0.96

In conclusion, with a sample size of 300, the study is able to detect a 17% difference between median antibody titers with 80% power.

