5.2.2 STUDY/VISIT SCHEDULE

5.2.2.1 Day 1: main study visit

Participants will be informed of the study's objectives and design; if they agree, an informed consent form will be signed. After inclusion, the main study procedures will take place (questionnaire, sampling and follow-up).

The following variables will be collected:

- **Socio-demographic variables :**

- Age
- Gender
- Profession
- Civil status
- Study level

- **Medical history**

PROTOCOL: MALARIA AS A PROTECTIVE FACTOR AGAINST SEVERE COVID-19 IN THE DEMOCRATIC REPUBLIC OF CONGO

- Comorbidities: diabetes, tuberculosis, cancer, HIV, renal failure, chronic liver disease, chronic lung disease, heart disease
- Medicines
- Smoking
- Pregnancy
- **Clinical variables :**
 - Clinical status according to WHO scale
 - Duration of symptoms
 - Type of symptoms
 - Size
 - Weight
 - Blood Pressure
 - Heart Rate
 - Respiratory Rate (RR)
 - Temperature (T°)
 - Free Oxygen Saturation (SaO)₂
 - Spleen size

The following biological samples will be collected:

- 30 ml of venous blood will be collected using Lithium-Heparin vacutenaire tubes for the various immunological analyses (described below).
- 5 µl of capillary blood will be taken for the thick smear, two µl of blood for the thin smear (GE/FM) and one drop of blood for the TDR.

The results of the thick drop and RDT will be communicated to the attending physicians for hospitalized patients (cases). For outpatients (controls), the results will be communicated to the ZS team in charge of malaria management, in accordance with national guidelines.

Day 7 +- 2: follow-up

For controls: a telephone contact on Day 7 with the treating clinician or the patient will be considered in order to obtain information on their clinical evolution. If, in the meantime, they have developed severe COVID-19, they will be excluded from the study and will no longer be considered as controls.

During participation in the study, the telephone number of the control as well as that of a close relative and the attending physician will be recorded in order to monitor the participant's health status. The patient's telephone number will be recorded separately in the patient identification register, which will be accessible only to local investigators. This

PROTOCOL: MALARIA AS A PROTECTIVE FACTOR AGAINST SEVERE COVID-19 IN THE DEMOCRATIC REPUBLIC OF CONGO

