6.2. ANALYSIS POPULATION SECONDARY

Only participants who did not violate any major criteria will be included in the secondary analysis (see Table 1).

Table 1:Protocol violationsclassified as minor or major

Violation of the	Minor/major violation	Comments
Protocol Inclusion		
For CAS Criteria		
1. At least 18 years of age	Major	
2. Having an SARS-CoV infection confirmed by RT-PCR or rapid antigen test within 72 hours of inclusion.	Major	
3. Have given their informed consent or that of their guardian/ representative to participate in the study.	Major	
4. Clinical signs of pneumonia: fever, cough, dyspnea or crepitations and (Respiratory rate > 30 cycles/min or severe respiratory distress or SpO2 < 90% on room air)	Major	
5. Being admitted to a care unit for COVID-19	Major	
6. Reside in the health zone for at least 6 months	Minor	

For WITNESSES

1. Be at least 18 years old	Major
2. Have a PCR or antigenic test confirmed SARS-CoV- 2 infection within 72 hours prior to inclusion.	Major
3. Have given informed consent to participate in the study	Major
4. Be asymptomatic or symptomatic, but without any signs of severe pneumonia	Major
5. Not to be admitted to a care unit for COVID-19.	Major
6. Reside in the study health area for at least 6 months	Minor

Exclusion Criteria (CASES AND WITNESSES)

1. The subject has a contraindication at venipuncture, determined by clinical judgment	Major
2. The subject is vaccinated against SARS- CoV-2	Major
3. The subject has been infected with SARS- CoV-2 in the past and now presents with a reinfection	Major

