7. ANALYSIS

A conditional logistic regression model will be fitted with the logarithm of malaria antibody levels to Circum Sporozoite Protein (CSP) as the independent variable. The p-value for the test of no association between malaria antibody levels and case/control will be presented.

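### The primary analysis keeps participants who fail the criteria that define a case or a control, so labels known to be wrong enter the main comparison

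*SAP*

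**What the plan says.** SAP 6.1 consists of one rule: "All enrolled participants will be included in the primary analysis". SAP 6.2 adds: "Only participants who did not violate any major criteria will be included in the secondary analysis", and Table 1 grades each entry criterion as Major or Minor.

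Two of the Major items set the group label. For cases, item 4 begins: "Clinical signs of pneumonia: fever, cough, dyspnea or crepitations and (Respiratory rate > 30 cycles/min or severe respiratory distress" (it continues with a low oxygen saturation on room air). For controls, item 4 is: "Be asymptomatic or symptomatic, but without any signs of severe pneumonia". Item 2, confirmed SARS-CoV-2 infection within 72 hours of inclusion, is also Major and applies to both groups.

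The primary model (SAP 7) is a conditional logistic regression on log anti-CSP IgG: "The p-value for the test of no association between malaria antibody levels and case/control will be presented".

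The protocol has one related rule. In 5.2.2.1, Day 7 follow-up, it says of controls who have developed severe COVID-19: "they will be excluded from the study and will no longer be considered as controls". SAP 6.1 and Table 1 do not repeat it. SAP 11 deals only with missing data.

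**The concern.** Analysing everyone enrolled protects a randomised comparison, because dropping people after randomisation can upset the balance that it created. This study has no randomisation to protect. Being severe or non-severe is the outcome of the primary model, and item 4 is its definition. A case who never had the severity signs, set against non-severe controls, contributes no severe versus non-severe contrast, yet is counted as if it did. The same holds for a control with severe signs. A person without confirmed infection belongs in neither group.

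The study will know about these errors, because Table 1 requires them to be recorded. At stake are a primary odds ratio diluted by avoidable misclassification and some loss of power. The population meeting the definitions is also never clearly attached to the primary question: the SAP does not say whether the 6.2 set is applied to the CSP comparison or only to the secondary objectives.

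**Working it through.** **Inputs from Protocol 5.1.5.** 100 cases and 200 controls, two controls per case; SD of log titre 1 in both groups; case-control correlation 0.7; "two-tailed test at the 5% significance level"; log means 6.8 (controls) and 6.61 (cases), a difference of 0.19; stated power 80% in the text and 0.81 in the table.

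**Assumptions not in the documents.** The correlation between two controls of a set is also 0.7. A mislabelled case has the antibody distribution of the non-severe, and a mislabelled control that of the severe. Label errors are unrelated to antibody level. The error rates are illustrative, since none is given.

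**Step 1: reproduce the plan's figure.** Variance of a case minus the mean of its two controls = 1 + (1 + 0.7)/2 − 2 × 0.7 = 0.45. SE = √(0.45/100) = 0.0671. Power = Φ(0.19/0.0671 − 1.96) = 0.809. Two simulation runs of the 1:2 conditional logistic regression (8,000 replicates each) gave 0.793 and 0.808. The plan's 0.81 is reproduced.

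**Step 2: keep the mislabelled people.** With shares c of cases and k of controls mislabelled, the expected difference is 0.19 × (1 − c − k).
- Combined 5%: 0.1805; power Φ(0.1805/0.0671 − 1.96) = 0.77.
- Combined 10%: 0.171; power 0.72 (simulated 0.71). The apparent difference in medians is 1 − exp(−0.171) = 15.7%, instead of 1 − exp(−0.19) = 17.3%.
- Combined 20%: 0.152; power 0.62 (simulated 0.60 to 0.61); apparent difference 14.1%.

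The simulated median log odds ratio per log unit moves from −0.63 to −0.57 at 10% and −0.50 at 20%, which are odds ratios of 0.53, 0.57 and 0.61.

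**Step 3: remove them.** The difference stays 0.19 under this model, but information is lost. A set with one remaining control has variance 1 + 1 − 2 × 0.7 = 0.60. Information = 100(1 − c) × [(1 − k)²/0.45 + 2k(1 − k)/0.60], and power = Φ(0.19 × √information − 1.96).
- For c = 10%, k = 0: 90/0.45 = 200; Φ(0.19 × 14.14 − 1.96) = 0.77.
- For c = k = 10%: 90 × (1.8 + 0.3) = 189; Φ(0.19 × 13.75 − 1.96) = 0.74.

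| Assumed mislabelling | Kept | Removed |
|---|---|---|
| 5% of cases | 0.77 | 0.79 |
| 10% of cases | 0.72 | 0.77 |
| 20% of cases | 0.62 | 0.72 |
| 5% of cases and 5% of controls | 0.72 | 0.78 |
| 10% of cases and 10% of controls | 0.62 | 0.74 |

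**Step 4: the SAP's one control per case.** SAP 5 and 5.2 recruit a single control. With 100 pairs, SE = √(0.60/100) = 0.0775 and power before any mislabelling is 0.69. With 5%, 10% or 20% of cases mislabelled, it is 0.64, 0.60 or 0.50 if they are kept, and 0.67, 0.64 or 0.59 if those pairs are removed. The ordering is the same from a lower start.

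**The case against.** The strongest reply is that such people should be rare. Protocol 5.1.3 checks severe cases for eligibility before inviting them, and 5.1.4 draws controls from a register of RT-PCR positives. The cleaner population is already specified in SAP 6.2, so the dispute is partly about which set is called primary. The likely rarity stands: no rate is given, and at a very low rate the effect is negligible. It does not remove the gap, because Table 1 exists precisely for enrolled people who fail a criterion, and 6.1 tells the analyst to keep them.

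Several stronger readings are tempting and are not supported.

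- **Every Major violation is a wrong label.** Age, consent, venipuncture, vaccination and reinfection do not change severity status. A positive test just outside the 72-hour window leaves the label correct. A control admitted to a care unit without severe signs is still non-severe by item 4. Only item 4 failures clearly mislabel, and unconfirmed infection makes study membership wrong.
- **The loss is measured from 0.81.** That figure assumes no violations, and removal costs sets. In the case-only scenarios the gain from removal is about 2, 5 and 10 points at 5%, 10% and 20%, not the 4, 9 and 19 points obtained by comparing with 0.81.
- **The odds ratio must move towards 1.** That needs label errors unrelated to antibody level. A patient admitted with pneumonia just short of a threshold need not resemble community controls.
- **People who never consented would be analysed.** Consent precedes questionnaire and sampling (Protocol 5.1.4, 5.2.2.1, 8.3), so someone who never consented should have no CSP value. What remains is consent later found invalid, which the SAP should still cover.

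The Day 7 rule does not close the gap, since it concerns later progression rather than signs present at inclusion.

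**Conclusion.** The concern holds in a limited form. As written, the primary model analyses people under a case or control label that the study knows to be wrong, and no other rule reclassifies or removes them. The plan also treats like situations differently: a control who becomes severe by Day 7 leaves the study, while one who already had severe signs at inclusion stays in the primary analysis.

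The actual size is unknown. Under the assumed rates and independent label errors, removing these people gains roughly 2 to 12 points of power over keeping them in the 1:2 design, and leaves the 0.19 difference undiluted. A reader might infer that the primary result is invalid or that power would be restored to 0.81; the documents support neither. This is an inexpensive improvement to the analysis population, not a flaw that defeats the study.

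**What to change.** In SAP 6.1, define the primary population as participants with valid consent who meet the group-defining criteria: confirmed SARS-CoV-2 infection, and the severity signs for cases or their absence for controls. State that the protocol's Day 7 exclusion applies. A missed 72-hour window alone should not remove anyone from this population.

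State the rule for broken sets. Drop each failing individual, including a failing second control, and keep a matched set only if its case and at least one control remain.

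Run the same CSP comparison, as named sensitivity analyses, on all enrolled participants with valid consent and on the 6.2 population without Major violations. This also settles whether 6.2 applies to the primary question.

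The cost is SAP wording and a few matched sets lost from the primary analysis. With one control per case, each failing control costs a whole pair. The change belongs before the SAP is finalised, which SAP 1 places before database lock; a major change after that has to be justified in the analysis report.

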6.2. ANALYSIS POPULATION SECONDARY

Only participants who did not violate any major criteria will be included in the secondary analysis (see Table 1).

Table 1:Protocol violationsclassified as minor or major

Violation of the	Minor/major violation	Comments
Protocol Inclusion		
For CAS Criteria		
1. At least 18 years of age	Major	
2. Having an SARS-CoV infection confirmed by RT-PCR or rapid antigen test within 72 hours of inclusion.	Major	
3. Have given their informed consent or that of their guardian/ representative to participate in the study.	Major	
4. Clinical signs of pneumonia: fever, cough, dyspnea or crepitations and (Respiratory rate > 30 cycles/min or severe respiratory distress or SpO2 < 90% on room air)	Major	
5. Being admitted to a care unit for COVID-19	Major	
6. Reside in the health zone for at least 6 months	Minor	

For WITNESSES

1. Be at least 18 years old	Major
2. Have a PCR or antigenic test confirmed SARS-CoV- 2 infection within 72 hours prior to inclusion.	Major
3. Have given informed consent to participate in the study	Major
4. Be asymptomatic or symptomatic, but without any signs of severe pneumonia	Major
5. Not to be admitted to a care unit for COVID-19.	Major
6. Reside in the study health area for at least 6 months	Minor

Exclusion Criteria (CASES AND WITNESSES)

1. The subject has a contraindication at venipuncture, determined by clinical judgment	Major
2. The subject is vaccinated against SARS- CoV-2	Major
3. The subject has been infected with SARS- CoV-2 in the past and now presents with a reinfection	Major

7. ANALYSIS

A conditional logistic regression model will be fitted with the logarithm of malaria antibody levels to Circum Sporozoite Protein (CSP) as the independent variable. The p-value for the test of no association between malaria antibody levels and case/control will be presented.

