7 DATA ANALYSIS

A detailed statistical analysis plan will be developed prior to completion of the statistical analysis. The analysis plan will provide a full description of the variables of interest, statistical methods (including management of missing data, statistical adjustment, management of confounding factors and interactions), subgroup definitions and sensitivity analyses.

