1. INTRODUCTION

This Statistical Analysis Plan (SAP) provides a detailed and comprehensive description of the main pre-planned analyses for the study "Malaria as a protective factor against severe forms of COVID-19 in DRC". The high prevalence of malaria in sub-Saharan Africa may play a role, according to some studies, in a possible protection against the severity of COVID-19 in endemic areas. However, the scientific evidence for the physiological role of this "induced" immunity is not established. We wish to conduct this study to elucidate this hypothesis. Details on the conduct of the study are described in the protocol.

These planned analyses will be carried out by statisticians from the Clinical Research Centre (CRC/INRB) and the Clinical Trials Unit of the Institute of Tropical Medicine (CTU ITM, Antwerp). The results of the analysis will be described in a statistical analysis report, which will serve as the basis for major research publications. This document describes the statistical methods for the primary and secondary objectives of the study as defined by the protocol. Additional analyses may be performed but are not covered by the current analysis plan.

This analysis plan will be finalised and approved before the database of the first analyses is locked. Major changes in the statistical methodology used for the main and pre-planned analyses of this SAP require a detailed description and justification in the Statistical Analysis Report (SAR). The dataset, programmes and final results are archived in accordance with Good Clinical Practice guidelines (ICH E9).

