2.2. OBJECTIVES

THE MAIN OBJECTIVE:

is to investigate whether the immunity conferred by Plasmodium protects against severe forms of COVID-19. This will be done by comparing Plasmodium antibody levels in severe and non-severe COVID-19 cases.

SECONDARY OBJECTIVES

They are :

- Comparing the cellular response against malaria between severe and non-severe COVID-19 cases
- To compare the proportions of acute malaria infection between severe and non-severe cases of COVID-19 using the Thick Gauge (TG) and Rapid Diagnostic Test (RDT)
- Describe the clinical characteristics and status of severe and non-severe cases of COVID-19 with and without malaria exposure
- To assess the modulating impact of existing antimalarial immunity on the strength of humoral and cellular immune responses to SARS-COV-2 in severe and non-severe cases of COVID-19
- Compare the SARS-COV-2 specific cellular immune response between severe and non-severe cases
- Assessing the modulatory impact of antimalarial immunity on induced immunity using specific antiviral receptor stimulations of the innate immune system

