3. HYPOTHESES OF THE STUDY

Anti-malarial immunity would play a protective role against severe forms of COVID-19.

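### The protocol leaves confounding to the SAP, but the SAP pre-specifies no confounder-adjusted model to support a claim of protection

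*SAP*

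**What the plan says.** Protocol section 7 promises that the SAP will describe, among other methods, "statistical adjustment, management of confounding factors and interactions), subgroup definitions and sensitivity analyses". Protocol 7.1 then fixes the primary model: conditional logistic regression with log anti-CSP as the only independent variable. Protocol 5.1.5 powers that model.

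SAP section 7 restates it: "A conditional logistic regression model will be fitted with the logarithm of malaria antibody levels to Circum Sporozoite Protein (CSP) as the independent variable". The only result it names is a p-value: "The p-value for the test of no association between malaria antibody levels and case/control will be presented". The secondary and exploratory conditional logistic models (SAP 8 and 9) also have one independent variable each. No SAP section names a confounder, an adjusted model or an adjusted sensitivity analysis. On anything further, SAP section 1 says: "Additional analyses may be performed but are not covered by the current analysis plan".

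The aim is causal in tone. The main objective "is to investigate whether the immunity conferred by Plasmodium protects against severe forms of COVID-19" (SAP 2.2), and the hypothesis reads "Anti-malarial immunity would play a protective role against severe forms of COVID-19" (SAP 3).

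The Day 1 visit (Protocol 5.2.2.1) collects "Comorbidities: diabetes, tuberculosis, cancer, HIV, renal failure, chronic liver disease, chronic lung disease, heart disease", as well as smoking, profession and level of education.

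**The concern.** Cases are inpatients of COVID-19 treatment centres; controls are non-severe cases from the same Health Zone. The two groups may differ in chronic illness or social position, and either may also go with malaria exposure and so with anti-CSP level. Conditioning on the matched sets does not remove such differences.

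The association could then show protection that is not there, or hide protection that is. A bare p-value gives neither direction nor size. If an adjusted model is first chosen after the data are seen, its covariates will carry less weight than a list fixed before lock, and the SAP as written would class that model as unplanned.

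**Working it through.** **What is and is not controlled**

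| Factor | Handling |
|---|---|
| Sex, Health Zone | matched |
| Age | matched within 5 years (protocol) or 10 years (SAP); not in the model |
| Vaccination, previous SARS-CoV-2 infection | excluded |
| Comorbidity, smoking, education, profession | collected; not matched, in no model |

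The last row is also absent from the clinical-features list in SAP 4.2, so the case-versus-control table in SAP 8 need not show an imbalance.

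**Reproducing the plan's power.** Inputs from Protocol 5.1.5: 100 cases, 200 controls, SD 1, correlation 0.7, log means 6.8 and 6.61, two-sided 5%. The within-set variance is 1 − 0.7 = 0.3. SE = √[0.3 × (1/100 + 1/200)] = 0.067. Power = Φ(0.19/0.067 − 1.96) = 0.81; the table states 0.81. Simulating the single-term conditional logistic model gives about 0.80. The stated power therefore belongs to the crude model with two controls per case. SAP section 5 has one control per case; with 100 pairs, simulated crude power is about 0.66. Both ratios are shown below.

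**Illustration of bias.** Every covariate size here is assumed: one binary confounder in 40% of cases and 20% of controls, with no true effect. The spurious shift is (0.40 − 0.20) × gap, where the gap is how much lower log anti-CSP is in people with the confounder.

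| Gap (fall in median) | Spurious shift | Share of 0.19 | Crude rejection 1:2 | Crude rejection 1:1 | Crude OR per log unit |
|---|---|---|---|---|---|
| 0.10 (10%) | 0.02 | 11% | about 6% | about 5–6% | 0.94 |
| 0.25 (22%) | 0.05 | 26% | about 11% | about 8–9% | 0.85 |
| 0.50 (39%) | 0.10 | 53% | about 28% | about 21% | 0.74 |

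With the confounder recorded correctly and in the model, rejection is about 5% throughout. The 0.50 gap is large: 0.50/√0.3 = 0.9 within-set SD.

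**Opposite direction.** With a true shift of 0.19 and comorbid people 0.25 higher, power is about 0.53 crude against 0.77 adjusted (1:2), and 0.40 against 0.62 (1:1).

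**Poorer recording in cases.** Protocol 5.2.1 takes information from the medical file when a case cannot communicate. At gap 0.50, suppose comorbidity is captured in 95% of affected controls. If it is captured in 80%, 70% or 50% of affected cases, the adjusted test rejects in 9%, 14% or 29% (1:2) and 7%, 11% or 20% (1:1). The last is no better than crude.

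**Power of the adjusted model at shift 0.19**, with binary covariates unrelated to anti-CSP. Ranges reflect separate simulation runs.

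| Covariates (cases/controls) | 1:2 | 1:1 |
|---|---|---|
| none (crude) | 0.80 | 0.66 |
| one, 40/20% | 0.75–0.79 | about 0.62 |
| one, 50/10% | 0.64 | about 0.49 |
| three, each 40/20% | 0.70–0.72 | about 0.53 |
| four, each 40/20% | about 0.69 | about 0.49 |

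**The case against.** The SAP follows the protocol's primary analysis exactly. A reader might infer that the SAP dropped an adjusted primary model; it did not, because Protocol 7.1 never had one. What is missing is the description of adjustment and confounding that protocol section 7 promised.

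A reader might also infer that nothing beyond age and sex is controlled. That is too strong. The exclusions remove vaccinated and previously infected people, both groups are infected adults, and Health Zone matching plausibly absorbs part of the urban to peri-urban malaria gradient. None of this reaches individual comorbidity, smoking, education or profession.

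The strongest objection concerns size. Every confounder figure above is assumed, the smallest gap does almost nothing, and the striking result needs a large one. This stands: the illustration shows what could happen, not what will.

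Adjustment is not free or complete either. It costs power when covariates predict severity strongly, and it fails if comorbidity is recorded much less fully in cases. A single yes/no comorbidity variable pools conditions that need not relate to anti-CSP in the same direction, so some confounding may remain. These are reasons to make the adjusted model a supporting analysis with a short list, not to omit it.

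**Conclusion.** The concern holds as an unmet commitment that bears on the main conclusion: the protocol assigns confounding to the SAP, and the SAP pre-specifies nothing. It should be fixed.

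The crude model remains a legitimate, powered test of association within matched sets. It cannot by itself support a statement that malaria immunity protects. It would be tempting to go further and call the primary result biased, or biased towards protection. The documents do not support that, since they give no covariate prevalences and no relation between any covariate and anti-CSP. Under the assumed 40% versus 20% imbalance, false rejection ranges from about nominal to 28% (1:2) or 21% (1:1), and confounding the other way could hide a real effect.

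Reporting only a p-value is a smaller, separate gap that the same change can close.

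**What to change.** SAP section 1 says: "This analysis plan will be finalised and approved before the database of the first analyses is locked". Before that lock, amend SAP section 7 as follows.

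- Keep the crude conditional logistic model as the powered primary test.
- Add one supporting conditional logistic model of case status on log anti-CSP, adjusted for age in years, any chronic comorbidity (yes/no), current smoking (yes/no) and education level. Do not adjust for signs that define case status, such as respiratory rate or oxygen saturation.
- Report the odds ratio per log unit with 95% CI for both models.
- State that a claim of protection must rest on the adjusted estimate as well as the crude one. A change of sign, or a change in the log odds ratio above a threshold fixed in the SAP (for example 20%), is reported as possible confounding. A relative threshold is unstable when the crude estimate is near zero, so show both intervals beside it.
- Add these covariates, with numbers missing per group, to the case-versus-control table.

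The differing age bands and control ratios in the two documents need separate reconciliation.

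**Cost.** SAP wording and one model on data already collected. The adjusted model has less power, by an amount that depends on how strongly the covariates predict severity (last table under the working). Missing covariates also remove sets. With an assumed 10% of participants incomplete, 0.9 × (1 − 0.1²) = 89% of 1:2 sets keep the case and at least one control, and 0.9² = 81% of pairs remain at 1:1. The crude test is unaffected.
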